#### **Table 3:** SAEs that do not require reporting

All events which meet the definition of serious must be recorded in the participant medical notes, including the causality and severity, throughout the participant's time on trial, including follow-up, but for trial purposes these events do not require reporting on the SAE Form. Such events are "safety reporting exempt".

#### 10.4.2. SAEs requiring non-expedited reporting

Where the safety profile is well established, the causal relationship between the intervention (or the participant's underlying condition), and the SAE, may be known. That is, such events are protocol-defined as "expected".

Such events should still be recorded by the site research team in the participant's medical notes and reported to the ERASER Trial Office, but it does not require expedited reporting (immediately on the site becoming aware of the event) since the assessment of expectedness for the specified events has been pre-defined. These SAEs can be reported alongside follow up CRFs at 1 or 3 months post randomisation. These expected SAEs are listed in Table 4 below.

Expected SAE ID	Expected SAE	Process
01	Hospital admissions lasting less than 24 hours	
02	Death - The cause of which is unrelated to intervention	
03	Organ failure – as indicated by SOFA score	
04	Infection to insertion site	Report on SAE Form and
05	Sepsis	provide to the ERASER Trial Office along with follow-up
06	Septic shock	CRFs.
07	Failure of extubation attempt	
08	New clinical diagnosis of pneumonia	
09	Primary cardiac bradyarrythmias and tachyarrythmias	

Table 4: ERASER Trial SAEs requiring non-expedited reporting

#### 10.4.3. SAEs requiring expedited reporting

All SAEs not listed in section 10.4.1 and 10.4.2 must be reported to the ERASER Trial Office on a trial specific SAE Form within 24 hours of the site research team becoming aware of the event. Examples of SAEs that would require expedited reporting can be found in the table 5 below.

Please note: This list is **not** exhaustive.

**Table 5:** Examples of ERASER Trial SAEs that require expedited reporting

Expected SAE	Process
Anaesthetic toxicity	
Primary cardiac bradyarrythmias and tachyarrythmias where local investigators believe the cause local anaesthetic	Report on SAE Form and provide to the ERASER Trial Office within 24 hours of becoming aware of the event.

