## 1.2. TRIAL RATIONALE

Patients with MRF require a simple, safe, effective, and universally available analgesic option. Serratus Anterior Plane Block (SAP) is a new technique placed under ultrasound guidance where the catheter is inserted in the lateral chest wall between latissimus dorsi and serratus anterior muscles in the midaxillary line. It blocks the pain caused by MRF and has the potential to provide a simple, easy, safe, and effective analgesic delivery technique in most patients for up to 10 days (10).

The CI, along with collaborators, conducted a cross-sectional cohort study on SAP. Using the Trauma Audit and Research Network database, 203 patients admitted to two Major Trauma Centres with MRF who received regional analgesia between 2016-2018 were included in the study (11). The primary outcome was a change in pain scores (0=no pain, 1=mild pain, 2=moderate pain, 3=severe pain) and inspiratory volumes (ml) pre- and post-regional analgesia. SAP Catheter, PA Catheter and TEA Epidural were assessed. The results showed an improvement in inspiratory volumes and a reduction in pain scores across all groups. Inspiratory volumes in the SAP group increased from (mean  $\pm$  standard deviation (SD)) 959 mls  $\pm$ 726 to 1667 mls  $\pm$  713 mls (p<0.001). Pain scores with SAP block significantly

reduced from moderate/severe to mild/moderate  $2.42 \pm 0.96$  to  $1.14 \pm 0.81$  (p<0.01). A similar increase in inspiratory volumes and reduction in pain scores was observed with PA and TEA, but with no statistically significant difference between the groups. These results suggest that post block SAP analgesia improves inspiratory volumes and reduces pain scores similar to PA or TEA. SAP catheters have the potential to radically increase the accessibility of regional analgesia to patients with MRF, similar to the impact of fascia iliac blocks for hip fracture pain. International societies have advocated that a high-quality prospective trial is urgently needed (12). The proposed pragmatic multicentre randomised controlled trial (RCT) comparing SAP to usual care would provide conclusive evidence to address clinicians' moral and ethical dilemmas during pain management after MRF.

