## 10.4. SERIOUS ADVERSE EVENTS IN ERASER

It is recognised that the frequency of SAEs in this participant population may be high. Many of these SAEs will be anticipated due to the potential severity of the trauma experienced by the participant. We have therefore outlined anticipated SAEs that do not require reporting and anticipated SAEs that do not require expedited reporting. For all SAEs, the PI or delegate must do one of the following:

- **Record safety reporting-exempt SAEs** in the medical notes but not report them to the Trial Office on an SAE form as per Table 3.
- **Report SAEs in a non-expedited manner** to the Trial Office for the pre-defined subset of SAEs as per Table 4.
- **Report SAEs in an expedited manner** (within 24 hours of the site research team becoming aware of the event) to the Trial Office for SAEs not covered by the above 2 categories as per Table 5.

**Note:** when an SAE occurs at the same hospital at which the participant is receiving the trial intervention or is being followed up for trial purposes, processes must be in place to make the site research team aware of any SAEs, regardless of which department first becomes aware of the event, in an expedited manner.

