#### 10.4.1. SAEs not requiring reporting

Several events that meet the definition of an SAE will not require reporting on the trials dedicated SAE form. If any of the events outlined below in table 3 occur during an individual's participation, from the date that trial intervention started through to end of follow-up, reporting the event on a SAE form is not required as the SAE is not considered to be critical to evaluations of the safety of the trial.

Expected SAE	Process
Pre-planned hospitalisation	Document in medical notes only
SAEs relating to a pre-existing medical condition or those that have occurred as a result of the participants injuries which are unrelated to MRF	Document in medical notes only

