#### 10.4.5. Assessment of causality

When completing the SAE Form, the PI or an appropriately qualified delegate, will be asked to define the nature of the seriousness (see Table 7) and causality (relatedness; see Table 6) of the event.

In defining the causality, the PI must consider if any concomitant events or medications may have contributed to the event and, where this is so, these events or medications should be reported on the SAE form. It is not necessary to report concomitant events or medications which did not contribute to the event.

All events considered possibly, probably or definitely related to the intervention will be reported as 'related'; all events considered to be unlikely or unrelated to the intervention will be reported as unrelated.

The same categorisation should be used when describing AEs and protocol-exempt SAEs in the medical notes.

Category	Definition	Causality	
Dofinitoly	There is clear evidence to suggest a causal relationship, and other possible		
Demnitely	contributing factors can be ruled out.		
Brobably	There is evidence to suggest a causal relationship, and the influence of other		
Probably	factors is unlikely.		
	There is some evidence to suggest a causal relationship. However, the		
Possibly	influence of other factors may have contributed to the event (e.g., the		
	participant's clinical condition, other concomitant events or medication)		
	There is little evidence to suggest there is a causal relationship. There is		
Unlikely	another reasonable explanation for the event (e.g., the participant's clinical		
	condition, other concomitant events or medication).		
Not related	There is no evidence of any causal relationship.		

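### The SAE routing tables conflict on arrhythmia attributed to local anaesthetic, and Tables 3 and 4 largely ignore whether an event is related to the block

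*Protocol*

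**What the plan says.** Section 10.4 sorts SAEs into three routes: medical notes only (Table 3), an SAE form with the follow-up CRFs (Table 4), and an SAE form within 24 hours (Table 5). The third is defined as what remains. Section 10.4 reserves it "for SAEs not covered by the above 2 categories as per Table 5", and 10.4.3 repeats the rule: "All SAEs not listed in section 10.4.1 and 10.4.2 must be reported to the ERASER Trial Office".

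- **Table 3** (10.4.1) has two rows: pre-planned hospitalisation, and "SAEs relating to a pre-existing medical condition or those that have occurred as a result of the participants injuries", the latter qualified as not connected with the rib fractures.
- **Table 4** (10.4.2) has nine items. Item 02 is "Death - The cause of which is unrelated to intervention". Item 09 covers primary cardiac brady- and tachyarrhythmias without any condition. These events need no expedited report "since the assessment of expectedness for the specified events has been pre-defined".
- **Table 5** (10.4.3) gives examples for 24-hour reporting, including "Primary cardiac bradyarrythmias and tachyarrythmias where local investigators believe the cause local anaesthetic".

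Section 10.4.5 counts possibly, probably and definitely related events as related. Of exempt events it adds: "The same categorisation should be used when describing AEs and protocol-exempt SAEs in the medical notes". Section 10.4.8 has the chief investigator assess related SAEs for expectedness. Section 10.5.2 sends unexpected and related SAEs to the ethics committee, sponsor and university within 15 days of notification.

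**The concern.** A site following the tables literally cannot tell which route applies to a serious arrhythmia that it attributes to local anaesthetic. More generally, with one exception, the route depends on event type and not on whether the block may have caused the event.

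This matters because SAE forms are the main safety dataset. Section 10.3 does not require non-serious AEs to be reported to the trial team, and section 8.2.2 measures the safety outcome by SAE review. The chief investigator's causality review begins when a form arrives (10.4.5), and the DMC sees the SAE data that the Trial Office submits (10.5.1). An event left in the notes bypasses both. Where two rows fit, the choice falls to site staff who know the allocation (6.3).

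**Working it through.** The protocol gives no figure to reproduce here. The check is a reading of the tables side by side, a row count, and one calculation of timing.

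**1. Rows conditioned on relation to the intervention.** Table 3: 0 of 2. Table 4: 1 of 9 (item 02). Together: 1 of 11. Table 3 does carry a qualifier, but it refers to the rib fractures, not to the block.

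**2. Arrhythmia attributed to local anaesthetic.** Item 09 contains it, because item 09 contains all primary cardiac arrhythmias. It is therefore listed in 10.4.2, and the opening rule of 10.4.3 takes it out of the 24-hour route. Table 5, under that same rule, puts it in. If the patient also had prior conduction disease, Table 3 can be read to fit as well, which gives three candidate routes.

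**3. Related events of Table 4 type.** Take septic shock (item 06) judged related to an infected catheter. The item has no condition on cause, so the event is non-expedited. The introduction to 10.4.2 says that the known causal link may be with the intervention, and that such events are defined as expected. Section 10.4.8 calls an event unexpected if the protocol does not define it as expected. The event would thus ordinarily be classed related and expected, and 10.5.2 would not call for the 15-day report. The same holds for organ failure (03) and sepsis (05), and for related cases of 01 and 07.

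**4. Mixed-cause events and Table 3.** Take a pre-existing condition that the site thinks was possibly aggravated by the block. Under 10.4.5 possibly related counts as related. The event still relates to a pre-existing condition, so Table 3 fits and no form is sent. Section 10.4.5 asks for causality to be graded in the notes for exempt SAEs, so an event graded related can remain there.

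**5. Overlap of Tables 3 and 4.** Sepsis from an injury other than the rib fractures is notes-only under Table 3 and reportable as item 05. A pre-planned admission under 24 hours fits Table 3 row 1 and item 01. No order of precedence is given.

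**6. Timing.** Section 10.4.2 allows non-expedited SAEs to come with the 1- or 3-month CRFs, and Table 1 gives those visits a window of 7 days either side. Table 9 says 4 weeks from awareness. Consider an event on day 1, known that day, taking 1 month as 30 days, 3 months as 91 days, and submission at the end of the window (assumptions):

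| Rule | Latest report | Days after the event |
|---|---|---|
| 24-hour route | day 2 | 1 |
| Table 9: 1 + 28 | day 29 | 28 |
| 10.4.2, 1-month CRF: 30 + 7 | day 37 | 36 |
| 10.4.2, 3-month CRF: 91 + 7 | day 98 | 97 |

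The two non-expedited rules differ from each other, and for the arrhythmia in step 2 the candidate deadlines run from 1 to 97 days.

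**The case against.** The best defence is that Table 5 is meant as a specific exception to item 09, and many sites would read it so. That is probably the intent, but item 09 has no exception wording and the opening rule of 10.4.3 points the other way. The defence shows that the repair is small, not that the text is consistent.

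A second defence largely stands. Every Table 4 event goes on an SAE form, is graded for causality by the site and is reviewed by the chief investigator; the DMC may ask for any SAE. Survival status and SOFA are collected daily in hospital in both arms, outside SAE routing. Listing expected events by type is also a deliberate choice, since 10.4.2 openly includes links with the intervention.

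Three stronger readings are tempting and are not supported:

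- A reader might infer that an event caused purely by the block can be notes-only. It cannot: such an event is not a planned admission, does not relate to a pre-existing condition and does not result from another injury. Only mixed-cause events fall in the gap.
- A reader might infer that a related Table 4 event can never be unexpected. Table 8 defines unexpected as inconsistent with known information about the trial procedures, which leaves the chief investigator some room, although Table 2 and 10.4.8 point to listing by event type.
- A reader might infer that calling the block new in section 1.2 contradicts the established safety profile invoked in 3.3. Section 1.2 also cites six RCTs in a search broadened to postoperative patients, with no adverse events reported, and 3.3 says that both arms are in common UK use.

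**Conclusion.** The point holds as a conflict of wording with a limited safety consequence. One event type is assigned to two incompatible routes. Apart from death, Table 4 items stay non-expedited and pre-labelled expected even when judged related to the block; the harm there is delay and the likely loss of the 15-day report. Mixed-cause events under Table 3 can go without an SAE form or central review; there the harm is loss of the event from the SAE data.

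The protocol gives no basis for estimating how many events would be misrouted, so no rate is offered. The sample size, primary outcome and planned analysis are unaffected. The conclusion rests on reading 10.4.3 as written and on 10.4.5 counting possibly related events as related.

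**What to change.** Reconcile Tables 3, 4, 5 and 9 in one wording amendment:

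1. Reword item 09 to exclude arrhythmias attributed to local anaesthetic, in the form item 02 already uses. Using Table 5's own condition makes the two entries exact complements.
2. State that Table 3 exemptions do not apply to an SAE judged possibly, probably or definitely related to the intervention.
3. State whether related cases of items 01, 03, 05, 06 and 07 keep their non-expedited, expected status, or follow 10.4.3 with expectedness assessed individually. That choice is the sponsor's. Leave items 04 (insertion-site infection, block-related by nature) and 08 (pneumonia, the primary outcome event) expressly as listed.
4. State which row governs where Tables 3 and 4 overlap. Blanket precedence for Table 4 is not advised: it would make sepsis, organ failure and arrhythmia from other injuries or prior disease reportable, in a population where 10.4 expects SAEs to be frequent.
5. Give one timing for non-expedited SAEs in 10.4.2 and Table 9.

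For items 1 to 3 the cost is a few extra SAE forms or 24-hour reports, for events the site already attributes to local anaesthetic or judges related. Only patients given the block can have an event related to it, so counts of related events should not be read as a comparison between arms.

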#### 10.4.4. Follow up of pregnancy outcomes for potential SAEs

Known pregnancy at the time of randomisation is an exclusion criterion, however, in the unlikely event that a participant becomes pregnant during the course of the trial, this should be reported via the trial-specific Pregnancy Notification Form. There is no identified risk of congenital anomalies or birth defects in the offspring of participants as a result of their participation in the trial.

#### 10.4.5. Assessment of causality

When completing the SAE Form, the PI or an appropriately qualified delegate, will be asked to define the nature of the seriousness (see Table 7) and causality (relatedness; see Table 6) of the event.

In defining the causality, the PI must consider if any concomitant events or medications may have contributed to the event and, where this is so, these events or medications should be reported on the SAE form. It is not necessary to report concomitant events or medications which did not contribute to the event.

All events considered possibly, probably or definitely related to the intervention will be reported as 'related'; all events considered to be unlikely or unrelated to the intervention will be reported as unrelated.

The same categorisation should be used when describing AEs and protocol-exempt SAEs in the medical notes.

Category	Definition	Causality	
Dofinitoly	There is clear evidence to suggest a causal relationship, and other possible		
Demnitely	contributing factors can be ruled out.		
Brobably	There is evidence to suggest a causal relationship, and the influence of other		
Probably	factors is unlikely.		
	There is some evidence to suggest a causal relationship. However, the		
Possibly	influence of other factors may have contributed to the event (e.g., the		
	participant's clinical condition, other concomitant events or medication)		
	There is little evidence to suggest there is a causal relationship. There is		
Unlikely	another reasonable explanation for the event (e.g., the participant's clinical		
	condition, other concomitant events or medication).		
Not related	There is no evidence of any causal relationship.		

#### Table 6: Category and definition of SAE causality

#### Table 7: Category and definition of event seriousness

Severity	Definition
Mild	Awareness of signs or symptoms that do not interfere with the participant's usual activity is transient and resolved without treatment and with no sequelae.
Moderate	A sign or symptom which interferes with the participant's usual activity.
Severe	Incapacity with inability to do work or perform usual activities.

On receipt of a SAE Form, the ERASER Trial Office will forward it, with the unique reference number, to the CI or delegate who will independently\* review the causality of the SAE. A SAE judged by the PI or CI (or delegate) to have a reasonable causal relationship ("Related" as per table 6) with the intervention will be regarded as a related SAE. The severity and causality assessment given by the PI

will not be downgraded by the CI or delegate. If the CI or delegate disagrees with the PI's causality assessment, the opinion of both parties will be documented, and where the event requires further reporting, the opinion will be provided with the report.

\*Where the CI is also the reporting PI an independent clinical causality review will be performed.

## 10.4.6. SAE Reporting Procedure on SAE Form

On becoming aware that a participant has experienced a SAE which requires reporting, the PI or delegate should report the SAE to their own Trust in accordance with local practice and to the ERASER Trial Office.

For SAEs that are to be reported on a SAE Form, the PI or delegate must complete, date and sign the SAE Form. The completed form, together with any other relevant anonymised documents, should be submitted to the ERASER Trial Office (details below) in the timeline specified in section 10.4.2 and 10.4.3.

# To report an SAE, please complete the SAE Form on https://bctu-redcap.bham.ac.uk and notify the trial office at [contact]

**Please note:** If a paper SAE Form has been completed, the original must be retained in the ISF following entry onto the trial database.

Where an SAE Form has been completed by someone other than the PI initially, the original SAE Form will be required to be countersigned by the PI to confirm agreement with the causality and severity assessments.

On receipt of an SAE Form, the ERASER Trial Office will allocate each SAE a unique reference number and notify the site via email as proof of receipt. The site and ERASER Trial Office should ensure that the SAE reference number is quoted on all correspondence and follow-up reports regarding the SAE and filed with the SAE in the ISF.

If the site has not received confirmation of receipt of the SAE or if the SAE has not been assigned a unique SAE identification number within 1 working day, the site should contact the ERASER Trial Office.

#### 10.4.7. Provision of follow-up information

Where a SAE is reported, the participant should be followed up until resolution or stabilisation of the event. Follow-up information should be provided using the SAE reference number provided by the ERASER Trial Office. Once the SAE has been resolved, all critical follow-up information has been received and the paperwork is complete, a copy of the final version of the completed SAE form must be submitted to the ERASER Trial Office and the original kept in the ISF.

#### 10.4.8. Assessment of expectedness of an SAE by CI

The CI or delegate will assess all related SAEs for expectedness with reference to the criteria in table 8 below. If the event is unexpected (i.e. is not defined in the protocol as an expected event) it will be classified as an unexpected and related SAE.

The CI will undertake review of all SAEs and may request further information from the site for any given event(s) to assist this.

#### Table 8: Category and definition of AE expectedness

Category	Definition
Expected	An adverse event that is consistent with known information about the trial related procedures or that is clearly defined in the relevant safety information (i.e. ERASER protocol)
Unexpected	An adverse event that is not consistent with known information about the trial related procedures.

#### 10.5. REPORTING OF SAE BY TRIAL OFFICE

#### 10.5.1. Data Monitoring Committee

The ERASER Trial Office will submit SAE data for review by the committee, who may request and review any SAEs at the meetings.

#### 10.5.2. REC, Sponsor and University of Birmingham (UoB)

The ERASER Trial Office will submit a progress report to the Research Ethics Committee (REC), Sponsor, and UoB Research Governance Team (RGT) annually, starting 12 months after the date of initial REC favourable opinion. Any electronic copy should be emailed to the REC within 30 days of the end of the reporting period.

All events categorised as Unexpected and Related SAEs will be reported to these parties within 15 days of being notified.

